30 NOV 2023

RESEARCH & ETHICS COMMITTEE
[name]

Thus, a standardised approach to establish antibody concentration and function and its role in reducing neonatal disease is vital in achieving licensure of any future vaccines ³².

4.8. Group B streptococcus hexavalent polysaccharide conjugate vaccine [GBS6]

Pfizer is developing a hexavalent capsular polysaccharide (CPS) conjugate vaccine (group B streptococcus hexavalent polysaccharide conjugate vaccine [GBS6]) aimed at the prevention of group B streptococcal disease due to 6 serotypes (Ia, Ib, II, III, IV, and V) in young infants by active immunisation of pregnant women¹⁹. GBS6 has been developed based on Pfizer's historical experience with licensed and investigational polysaccharide conjugate vaccines, and published/public data with other investigational GBS CPS conjugate vaccines that have been evaluated in clinical trials, including a trivalent (Ia, Ib, and III) GBS CPS-cross-reactive material 197 (CRM₁₉₇) conjugate vaccine in pregnant women ³³. A phase 1/2, placebo-controlled, observer-blinded, dose-escalation trial, done at four clinical research centres in the USA in healthy, non-pregnant adults aged 18–49 years showed that the vaccine was well tolerated and elicited robust immune responses for all dose levels and formulations that persisted 6 months after vaccination ²⁰.

This Phase 2, randomised, placebo controlled, double blinded study will be the first evaluation of the investigational GBS6 in HIV-infected pregnant women. This study will enroll pregnant women with and without HIV to receive the GBS6 in order to provide an expanded safety and immunogenicity data set (for both pregnant women and their infants) and to support progression of the development of this vaccine.

4.9. Investigational Product

The investigational products are GBS6 and placebo (saline control). The GBS6 dose will be GBS6 20mcg without AlPO₄ (equivalent to 240 mcg/mL) 0.5mL dose or 20 mcg CPS/serotype).

A placebo controlled clinical trial investigating the safety and immunogenicity of GBS6 in pregnant women with and without human immunodeficiency virus (HIV) infection and their infants

Protocol Version 5.0, Dated 01/02/2023

Protocol Version/date 5.0,01/02/2023
R&D Protocol Code Number:
Page:26

5. Research Questions

5.1 Hypothesis

We hypothesise that the safety profile and tolerability of a hexavalent Group B Streptococcal vaccine is the same in women living with HIV and women who do not have HIV.

5.2. Primary, secondary and exploratory objectives

A. Primary Objectives

- A1. Primary Objective 1: To describe the safety and tolerability of GBS6 when administered at ≥ 27 0/7 to ≤ 35 6/7 weeks' gestation to pregnant women, with and without HIV, aged ≥ 18 to ≤ 40 years of age and their infants.
- A2. Primary Objective 2: To assess the safety of GBS6 in infants born to HIV positive and negative women who were vaccinated during pregnancy.

B. Secondary Objectives

- B1. Secondary Objective 1: To describe the immunogenicity of GBS6 when administered to pregnant women with and without HIV.
- B2. Secondary Objective 2: To describe GBS-specific antibody levels in infants born to women vaccinated with GBS6 during pregnancy.
- B3. Secondary Objective 3: To assess placental transfer of GBS-specific antibodies from pregnant women vaccinated with GBS6 to their infants.

C. Exploratory objectives

- C1. To describe the persistence of serotype-specific antibody responses to the GBS6 vaccine up to 12 months following delivery.
- C2. Exploratory Objective 2: To characterise GBS colonisation status in maternal participants

A placebo controlled clinical trial investigating the safety and immunogenicity of GBS6 in pregnant women with and without human immunodeficiency virus (HIV) infection and their infants

Protocol Version 5.0, Dated 01/02/2023

Protocol Version/date 5.0,01/02/2023
R&D Protocol Code Number:
Page:27

MAKERERE UNIVERSITY
SCHOOL OF MEDICINE
APPROVED AMENDMENT
Valid Until

★ 30 NOV 2023 ★

RESEARCH & ETHICS COMMITTEE
[name]

- C3. Exploratory Objective 3: To describe the immune responses in breast milk in women with and without HIV vaccinated with GBS6.
- C4. Exploratory Objective 4: To describe the immune responses to Expanded Programme on Immunisation (EPI) administered to HIV-exposed and unexposed infant participants born to maternal participants vaccinated with GBS6.
- C5. Exploratory Objective 5: To characterise GBS colonisation status in infant participants at birth, 6 weeks and 18 weeks of age.
- C6. Exploratory Objective 6: To explore GBS6 antibody levels from dried blood spots in infant participants at birth.

5.2 Primary, secondary and exploratory endpoints

Primary endpoints for primary objectives A1 and A2:

- Maternal primary endpoint 1: Occurrence of solicited local reactions within 7 days following administration of investigational product (pain at the injection site, redness, and swelling).
- Maternal primary endpoint 2: Occurrence of solicited systemic events within 7 days following administration of investigational product (fever, nausea/vomiting, diarrhoea, headache, fatigue/tiredness, muscle pain, and joint pain).
- Maternal primary endpoint 3: Occurrence of solicited and unsolicited adverse events through 1 month after administration of investigational product.
- Maternal primary endpoint 4: Occurrence of SAEs, MAEs, and obstetric complications (peripartum, intrapartum, and postpartum) throughout the study (Visit 1 through the 12month post-delivery study visit) and any unsolicited events leading to study withdrawal.
- Infant primary endpoint 1: Occurrence of unsolicited adverse events from birth to 6 weeks of age

A placebo controlled clinical trial investigating the safety and immunogenicity of GBS6 in pregnant women with and without human immunodeficiency virus (HIV) infection and their infants

Protocol Version 5.0, Dated 01/02/2023

Protocol Version/date 5.0,01/02/2023
R&D Protocol Code Number:
Page:28

- Infant primary endpoint 2: Occurrence of SAEs, AEs of special interest (major congenital anomalies, developmental delay, and suspected or confirmed GBS infection), and MAEs through 12 months of age and any unsolicited events leading to study withdrawal.

Secondary endpoints for secondary objectives B1, B2, B3:

- Maternal secondary endpoint 1: GBS serotype- specific IgG antibody titres measured at baseline, 2 weeks, 1 month after vaccination, at delivery and 6 weeks after delivery in HIV positive and HIV negative women.
- Maternal secondary endpoint 2: GBS serotype specific IgG titres measured at baseline, and at delivery in HIV positive and HIV negative women.
- Infant secondary endpoint 1: GBS serotype specific IgG antibody titres in HIV-exposed and unexposed infant participants measured at birth, 18 weeks and 12 months of life.
- Infant secondary endpoint 2: GBS serotype specific IgG titres in HIV-exposed and unexposed infant participants measured at 18 weeks of life.
- Infant secondary endpoint 3: Placental transfer ratio of GBS-specific antibodies in HIV-exposed and unexposed pregnancies.

Exploratory endpoints for exploratory objectives C1 to C6:

- Maternal exploratory endpoint 1: Fold increase in GBS serotype specific IgG antibody titres over baseline measured before vaccination through 12 months after delivery in HIV positive and HIV negative women.
- Maternal exploratory endpoint 2: Serotype specific GBS positive vaginal and/or rectal culture(s) before vaccination, at delivery, and 6 weeks after delivery in HIV positive and HIV negative women

A placebo controlled clinical trial investigating the safety and immunogenicity of GBS6 in pregnant women with and without human immunodeficiency virus (HIV) infection and their infants

Protocol Version 5.0, Dated 01/02/2023

Protocol Version/date 5.0,01/02/2023
R&D Protocol Code Number:
Page:29

- Maternal exploratory endpoint 3: GBS serotype specific IgG and IgA antibody titres in breast milk following vaccination of women living with HIV and their unexposed counterparts in colostrum (within 72 hours of delivery) and breast milk at 6 and 18 weeks after delivery
- Infant exploratory endpoint 1: IgG antibody titres to vaccines included in the extended programme of vaccination administered to HIV-exposed and unexposed infant participants as part of at 18 weeks and 12 months of age.
- Infant exploratory endpoint 2: Serotype specific GBS positive nasal/rectal cultures at delivery, 6 weeks and 18 weeks after delivery in infant participants.
- Infant exploratory endpoint 3 GBS serotype specific IgG antibody titres measured from dried blood spots in infant participants at birth.

A placebo controlled clinical trial investigating the safety and immunogenicity of GBS6 in pregnant women with and without human immunodeficiency virus (HIV) infection and their infants

Protocol Version 5.0, Dated 01/02/2023

Protocol Version/date 5.0,01/02/2023
R&D Protocol Code Number:
Page:30

6. Statistical design

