A placebo controlled clinical trial investigating the safety and immunogenicity of GBS6 in pregnant women with and without human immunodeficiency virus (HIV) infection and their infants

Protocol Version 5.0, Dated 01/02/2023

Protocol Version/date 5.0,01/02/2023
R&D Protocol Code Number:
Page:34

intervals for each group. Comparison between groups (GBS v Placebo within each HIV strata) will be by Fisher's exact test.

- Maternal primary endpoint 2:

Proportion of maternal participants reporting solicited systemic events within 7 days following administration of GBS6 vaccine will be calculated with exact binomial 95% confidence intervals for each group. Comparison between groups (GBS v Placebo within each HIV strata) will be by Fisher's exact test.

- Maternal primary endpoint 3:

Proportions of maternal participants reporting solicited and unsolicited adverse events through 1 month following administration of GBS6 vaccine will be calculated with exact binomial 95% confidence intervals for each group. Comparison between groups (GBS v Placebo within each HIV strata) will be by Fisher's exact test.

- Maternal primary endpoint 4:

Proportions of maternal participants with SAEs, MAEs, and obstetric complications (peripartum, intrapartum, and postpartum) throughout the study (Visit 1 through the 12-month postdelivery study visit) and any unsolicited events leading to study withdrawal following administration of GBS6 vaccine will be calculated with exact binomial 95% confidence intervals for each group. Comparison between groups (GBS v Placebo within each HIV strata) will be by Fisher's exact test.

- Infant primary endpoint 1:

Proportions of infants with unsolicited adverse events from birth to 6 weeks of age month following administration of GBS6 vaccine will be calculated with exact binomial 95% confidence intervals for each group. Comparison between groups (GBS v Placebo within each HIV strata) will be by Fisher's exact test.

A placebo controlled clinical trial investigating the safety and immunogenicity of GBS6 in pregnant women with and without human immunodeficiency virus (HIV) infection and their infants

Protocol Version 5.0, Dated 01/02/2023

Protocol Version/date 5.0,01/02/2023
R&D Protocol Code Number:
Page:35

- Infant primary endpoint 2:

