13.1 Participant paper diary card

The responsible research nurse/clinician will be asked to monitor and record local reactions reported by the participant, as well as, systemic events, including fever, and antipyretics/pain medication used to prevent and/or treat symptoms, within a fixed time window each day for 7 days following vaccination (where Day 1 is the day of vaccination) on a system that uses a personal digital assistant (PDA) or other technology. A baseline assessment (nausea/vomiting, diarrhea, headache, fatigue/tiredness, muscle pain, or joint pain over the previous month) prior to vaccination will be recorded in the paper diary card. This system, hereafter referred to as the participant's paper diary card, allows recording of these assessments only within a fixed time window, thus providing the accurate representation of the participant's experience at that time. Data on local reactions, systemic

A placebo controlled clinical trial investigating the safety and immunogenicity of GBS6 in pregnant women with and without human immunodeficiency virus (HIV) infection and their infants

Protocol Version 5.0, Dated 01/02/2023

Protocol Version/date 5.0,01/02/2023
R&D Protocol Code Number:
Page:88

events, and antipyretics/pain medication used to prevent and/or treat symptoms reported on the paper diary card will be uploaded manually entered into REDCap, where they will be available for review by investigators, their qualified designees, and sponsor staff at all times via an internet-based portal. At intervals agreed to by the sponsor, these data will be transferred electronically for analysis and reporting. These data do not need to be reported by the investigator in the CRF. However, if a participant withdraws because of prompted events reported in the paper diary card, the event(s) should be recorded on the AE page of the CRF, regardless of whether the investigator considers the event(s) to be clinically significant.

Investigators (or appropriately qualified designee) are required to review the paper diary card data online to evaluate participant compliance and as part of the ongoing safety review.

The investigator or designee must contact the participant in order to obtain stop dates for any reactions ongoing on the last day that the paper diary card was completed. The stop dates should be documented in the source documents and the information entered in the CRF.

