14.4. Withdrawal from the study due to Adverse events

Withdrawal due to AEs should be distinguished from withdrawal due to other causes, according to the definition of AE noted below, and recorded on the CRF.

When a participant withdraws from the study because of an SAE, the SAE must be recorded on the CRF and reported, as appropriate, on the CT SAE Report Form, in accordance with the Section 14.1, above.

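### The withdrawal component of maternal primary endpoint 4 is limited to unsolicited events, so a withdrawal caused by a solicited reaction is not counted as a withdrawal in any primary endpoint

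*Protocol*

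**What the plan says.** The synopsis (maternal primary safety endpoints) and Protocol section 5.2 define maternal primary endpoint 4 as SAEs, MAEs and obstetric complications throughout the study, plus "any unsolicited events leading to study withdrawal". Section 6.3 carries the same limit into the analysis: "any unsolicited events leading to study withdrawal following administration of GBS6 vaccine" is among the items to be reported as proportions with exact binomial 95% confidence intervals, with GBS6 compared with placebo within each HIV stratum by Fisher's exact test.

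The item just before it in section 5.2, maternal endpoint 3, names both classes of event: "Occurrence of solicited and unsolicited adverse events through 1 month after administration of investigational product".

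Two safety sections deal with withdrawal because of adverse events. Section 13.1 says that diary data need not be entered in the CRF by the investigator, but then makes an exception: "if a participant withdraws because of prompted events reported in the paper diary card, the event(s) should be recorded on the AE page", whether or not the investigator thinks them clinically significant. Section 14.4 says: "Withdrawal due to AEs should be distinguished from withdrawal due to other causes". It draws no line between solicited and unsolicited events.

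**The concern.** Primary Objective 1 covers tolerability as well as safety, and the stated hypothesis concerns tolerability in women with and without HIV. A woman leaving the study because of a vaccine reaction is a direct sign of poor tolerability. The protocol arranges to capture that information, yet the only maternal primary endpoint that counts withdrawals is worded so as to leave it out. A woman who leaves because of an unsolicited rash is counted in the withdrawal component. A woman who leaves because of a solicited headache or a sore arm is not.

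The limit is stated in three places, so an analysis plan that follows the protocol would inherit it. At stake is whether the reported proportion of women withdrawing because of adverse events is complete.

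**Working it through.** The protocol gives no figure for this component, so the main check sets the sections side by side.

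**1. Is the word limiting?** Endpoints 1 and 2 ("Occurrence of solicited local reactions within 7 days following administration of investigational product" and "Occurrence of solicited systemic events within 7 days following administration of investigational product") list the solicited events by name. Endpoint 3 says solicited and unsolicited when both are meant. Endpoint 4 says only unsolicited. The ordinary reading is that solicited events are outside its withdrawal component. The same phrase in infant primary endpoint 2 does no harm, because the protocol describes no solicited-event diary for infants.

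**2. Where does a reaction that leads to withdrawal appear?**

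| Primary endpoint | Reaction counted? | Counted as a withdrawal? |
|---|---|---|
| Maternal 1 or 2 | Yes, within 7 days | No |
| Maternal 3 | Yes, to 1 month | No |
| Maternal 4, SAE or MAE part | Only if it is an SAE or MAE | No |
| Maternal 4, withdrawal part | No, if it is solicited | No |

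**3. Which reactions are neither SAE nor MAE?** Section 14.10 defines an MAE as a non-serious AE that leads to assessment at a medical facility; it does not exclude solicited events. In Tables 3 and 4, Grade 4 pain and Grade 4 systemic events are defined by emergency-room attendance or admission, so these would enter endpoint 4. The notes to those tables say that reactions of Grade 3 or above are to be seen by the study site. Section 11.3, however, waives the visit if the woman cannot attend, the reaction has gone by the time of the call, the diary entry was wrong, or the investigator judges a visit unnecessary. Mild and moderate reactions are not on the section 11.3 list that prompts contact. The women left out of endpoint 4 altogether are therefore those who withdraw because of a mild or moderate reaction, or a severe one settled by telephone, that is not otherwise medically attended.

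**4. Scale.** The withdrawal rate is an assumption: 1% to 3% in a GBS6 group and none in placebo. Section 6.3 compares groups within HIV stratum, so the denominator is 75 (section 6.1).

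- Omitted women per GBS6 group = rate × 75: 0.01 × 75 = 0.75 and 0.03 × 75 = 2.25, or about 1 to 2.
- Over both GBS6 groups: 0.01 × 150 = 1.5 and 0.03 × 150 = 4.5.

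Exact (Clopper-Pearson) 95% limits for x of 75, and two-sided Fisher p for x/75 against 0/75:

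| x | Proportion | Exact 95% limits | Fisher p |
|---|---|---|---|
| 0 | 0% | 0 to 4.8% | 1.0 |
| 1 | 1.3% | 0.03% to 7.2% | 1.0 |
| 2 | 2.7% | 0.3% to 9.3% | 0.50 |
| 5 | 6.7% | 2.2% to 14.9% | 0.058 |
| 6 | 8.0% | 3.0% to 16.6% | 0.028 |

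Omitting 1 or 2 women changes the reported proportion and its interval. Against no placebo withdrawals, the test would cross 5% only at 6 of 75 (8%), well above the assumed range.

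**The case against.** The strongest reply is that little is lost. Solicited reactions are the whole of endpoints 1 and 2 and part of endpoint 3, each with exact intervals and a comparison with placebo. The withdrawal component can be read as a catch-all for events those endpoints might miss, such as an unsolicited event after 1 month. Many severe reactions would also reach endpoint 4 as MAEs, because women with them are to be seen at the site and the sites are a hospital and health centres. This largely stands. A reader might infer that the reaction vanishes from the primary safety analysis; it does not. What is missing is its count as a withdrawal. Whether a study-site visit makes a reaction an MAE is not stated, so the MAE route cannot be relied on to close the gap.

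It can also be said that sections 13.1 and 14.4 are recording rules, not endpoint definitions, and that unsolicited is never defined, so an event moved to the AE page might be analysed as one. Both points are fair. There is no formal contradiction between these sections and the endpoint, and the exclusion is the literal reading rather than a certainty. But the uncertainty means that two analysts could report different counts, which is itself a reason to settle the wording.

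Finally, the analysis plan could tabulate all AE-related withdrawals: adverse event is a listed withdrawal reason in section 11.4, and section 6.3 leaves detail to that plan. It could, but such a table would sit beside a primary endpoint whose definition still leaves these withdrawals out.

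**Conclusion.** The point holds as a matter of endpoint wording and is minor. Taken literally, no primary endpoint counts a withdrawal caused by a solicited reaction as a withdrawal, and women whose reaction is neither an SAE nor an MAE are missing from endpoint 4 altogether.

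Two stronger readings are not supported. A reader might infer that reactions are the likeliest vaccine-caused reason to leave the study; the protocol gives no withdrawal rates, and the vaccine is a single injection (section 9.3), so leaving avoids no further dose. A reader might also infer that the GBS6 against placebo comparison is biased towards no difference; that would require an excess of reaction-caused withdrawals on GBS6, which the documents neither state nor imply. The size given rests on the assumed 1% to 3% rate and on the literal reading of unsolicited. On those terms the effect is on a descriptive proportion. No power statement, sample size or error rate is touched.

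**What to change.** For maternal primary endpoint 4, in the synopsis, section 5.2 and section 6.3, replace "any unsolicited events leading to study withdrawal" with: *any adverse event, solicited or unsolicited, leading to study withdrawal*. Take the solicited cases from the AE-page entries that section 13.1 already requires. Infant endpoint 2 can stay as it is.

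The cost is a wording change in three places. No new data, procedure or participants are needed.

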6.1 Sample size

This is a Phase 2 randomised, placebo controlled, double-blinded study to assess safety, tolerability, and immunogenicity of GBS6 in pregnant HIV positive and HIV negative women and their infant participants. It will be the first evaluation of the investigational GBS6 vaccine in HIV-infected pregnant women. This study will enroll pregnant women with and without HIV to receive the GBS6 in order to provide an expanded safety and immunogenicity data set (for both pregnant women and their infants) and to support progression of the development of this vaccine. As such, the statistical analyses are largely descriptive and the sample size is chosen based on what is achievable at the site. Additionally, and consistent with the clinical phase of the study (II), the primary outcome is based on safety.

Regarding safety, for common pregnancy outcomes such as prematurity, this sample size of 300 in total would provide 80% power (5% alpha) to detect an increase in prematurity outcomes from a background rate of 10% in the placebo arm, to at least 22% in the vaccine arm.

For the secondary objectives of immunogenicity, approximately 300 pregnant women will be enrolled in this study, 150 participants at the selected GBS6 dose/formulation (75 HIV positive and 75 HIV negative) and 150 participants in the placebo group (75 HIV positive and 75 HIV negative). Based on data from a recent study (20), the standard deviation (SD) of the GMT responses to serotypes Ia, Ib and III is expected to be around 2.55 log e units.

With 75 women per group, the study will have at least 80% power (5% alpha) to detect at least 3.24-fold higher antibody responses post-vaccination in vaccinated participants compared with placebo.

A placebo controlled clinical trial investigating the safety and immunogenicity of GBS6 in pregnant women with and without human immunodeficiency virus (HIV) infection and their infants

Protocol Version 5.0, Dated 01/02/2023

Protocol Version/date 5.0,01/02/2023
R&D Protocol Code Number:
Page:31

	HIV-uninfected pregnant women	HIV-infected pregnant women
Placebo	Group 1 (n=75)	Group 3 (n=75)
GBS6 vaccine	Group 2 (n=75)	Group 4 (n=75)

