6.3 Statistical methods

Safety data will be analysed separately for maternal participants and their infant participants.

- Descriptive analysis

A flowchart will be used to summarise the number of mothers approached, consented, recruited, assigned to the different study arms, receiving the intended vaccines, completing the study protocol and analysed for the primary outcome, as recommended by the CONSORT statement (<http://www.consort-statement.org/>).

- Statistical significance and confidence intervals

A placebo controlled clinical trial investigating the safety and immunogenicity of GBS6 in pregnant women with and without human immunodeficiency virus (HIV) infection and their infants

Protocol Version 5.0, Dated 01/02/2023

Protocol Version/date 5.0,01/02/2023
R&D Protocol Code Number:
Page:33

MAKERERE UNIVERSITY
SCHOOL OF MEDICINE
APPROVED AMENDMENT
Valid Until

★ 30 NOV 2023 ★

RESEARCH & ETHICS COMMITTEE
[name]

5% significance will be used and 95% confidence intervals.

- Statistical software

Statistical analyses will be performed on STATA version 15 or similar.

- Missing data

Analysis will be by modified intention to treat (mITT), meaning individuals are analysed according to the group they are randomised to, but only those with at least one blood taken and antibody result will be included, with missing data (e.g. from withdrawals, non-compliers) assumed missing at random. Missing data will be excluded from relevant analyses. The mITT analysis will include blood samples taken outside the recommended timing. A per-protocol analysis will also be performed if there are major protocol deviations. Spurious data will be checked to source records and investigated but included if no cause is identified.

- Outliers, censored data and non-normal data

Outliers will be included in the analyses and investigated assuming no errors have occurred. We will assign all results of <2 a value of 1 for calculation of geometric means. Antibody concentrations will be log-transformed for analyses of mean antibody levels.

- Statistical analysis for each objective and outcome

Statistical Analysis of primary endpoints

The followings are the primary analyses for each of the outcomes related to primary objectives.

- Maternal primary endpoint 1:

Proportion of maternal participants reporting solicited local reactions within 7 days following administration of GBS6 vaccine will be calculated with exact binomial 95% confidence

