- Maternal exploratory endpoint 3: For each serotype, IgA/IgG GMCs will be calculated at all breast milk visits for each group with 95% confidence intervals. Groups 1 vs 2, 3 v 4 will be compared using similar methods to those for blood IgG concentrations.

- Infant exploratory endpoint 1: The proportion of infant participants achieving defined levels of IgG to diphtheria toxoid and 13-valent pneumococcal conjugate vaccine serotypes will be summarised descriptively at 18 weeks and 12 months of age. Groups 1 vs 2, 3 v 4 will be compared using similar methods to those for GBS IgG concentrations.

- Infant exploratory endpoint 2: Proportions of infant participants with GBS colonisation assessed by nasal/rectal swabs at birth and at 6 weeks and 18 weeks of age will be calculated with exact binomial 95% confidence intervals for each group. Comparison between groups (GBS v Placebo within each HIV strata) will be by Fisher's exact test.

- Infant exploratory endpoint 3: For each serotype, GMCs will be calculated from dried blood spots in infant participants at births for each group with 95% confidence intervals.

A placebo controlled clinical trial investigating the safety and immunogenicity of GBS6 in pregnant women with and without human immunodeficiency virus (HIV) infection and their infants

Protocol Version 5.0, Dated 01/02/2023

Protocol Version/date 5.0,01/02/2023
R&D Protocol Code Number:
Page:38

Note that detailed analyses of all the endpoints including additional exploratory analyses and graphical displays will be described in the SAP.

A placebo controlled clinical trial investigating the safety and immunogenicity of GBS6 in pregnant women with and without human immunodeficiency virus (HIV) infection and their infants

Protocol Version 5.0, Dated 01/02/2023

Protocol Version/date 5.0,01/02/2023
R&D Protocol Code Number:
Page:39

7. Trial design

This is a randomised, placebo controlled, double-blind, parallel group study which will be based at Kawempe Specialised National Referral Hospital, Kawaala and Komamboga Health Centre III and Wakiso and Kisenyi Health Centre IV, Uganda.

Subjects will be a randomized 1:1 to GBS6/placebo stratified by baseline HIV status:

1. HIV-uninfected women, placebo (saline) in pregnancy;
2. HIV-uninfected women, GBS6 in pregnancy;
3. HIV-infected women, placebo (saline) in pregnancy;
4. HIV-infected women, GBS6 in pregnancy;

	HIV-uninfected pregnant woman	HIV-infected pregnant woman

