9.3. Patient randomisation

Participants will be randomized to either receive one dose of GBS6 vaccine or Placebo as a single injection on Day 1.

Stratified Block randomization will be used in this study. Randomization will be done in blocks of eight (8) in an automated system of Stata, stratified by HIV status and the list uploaded in the REDCap database. Participants will be randomized onto either arm (trial vaccine or placebo) of the study at enrolment by the data manager. The groups within REDCap will be labelled (A and B) and only the data manager will have access to the randomization

A placebo controlled clinical trial investigating the safety and immunogenicity of GBS6 in pregnant women with and without human immunodeficiency virus (HIV) infection and their infants

Protocol Version 5.0, Dated 01/02/2023

Protocol Version/date 5.0,01/02/2023
R&D Protocol Code Number:
Page:49

MAKERERE UNIVERSITY
SCHOOL OF MEDICINE
APPROVED AMENDMENT
Valid Until

★ 30 NOV 2023 ★

RESEARCH & ETHICS COMMITTEE
[name]

CRF, but the data manager will not be aware of which group (A or B) is the trial vaccine or placebo. Equal numbers will be allocated into each group (total n=300, 75 per group), with randomisation stratified by HIV status.

During the screening visit, the Data Manager will enter the participant's Screening ID into the REDCap system and complete the Randomization eCRF to randomise a participant. Once the participant is randomised, the REDCap system will randomly allocate the participant to either arm A or B as above. This will be notified automatically to the unblinded pharmacist. The unblinded pharmacist will take the notification and prepare the vaccine/placebo accordingly. The participants will use the same randomisation number throughout the study. The pharmacist will retain the lists of the allocation of unblinded medication prepared. The list must be kept in a safe place away from the blinded study team and will be monitored by the unblinded monitor.

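### The 80% power for prematurity belongs to a pooled 150 v 150 comparison the protocol does not specify; its Fisher tests within each HIV stratum (75 v 75) have about 44%

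*Protocol*

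**What the plan says.** Protocol Section 6.1 (Sample size) gives one power statement for safety, which it describes as the basis of the primary outcome: "this sample size of 300 in total would provide 80% power (5% alpha) to detect an increase in prematurity outcomes". The rates it assumes are 10% on placebo and at least 22% on vaccine. It also says that the analyses are mainly descriptive and that the number of women was set by what the site can achieve.

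Section 6.3 (Statistical methods) sets a general level, "5% significance will be used and 95% confidence intervals", and then lists what it calls the primary analyses. Each of the four maternal and two infant primary endpoints gets a proportion with an exact binomial interval per group, followed by the same sentence: "Comparison between groups (GBS v Placebo within each HIV strata) will be by Fisher's exact test".

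Section 9.3 fixes the group sizes: "Equal numbers will be allocated into each group (total n=300, 75 per group), with randomisation stratified by HIV status". Each within-stratum comparison is therefore 75 v 75.

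Prematurity is not named among the endpoints in Section 5.2. The nearest is maternal primary endpoint 4: "Occurrence of SAEs, MAEs, and obstetric complications (peripartum, intrapartum, and postpartum) throughout the study".

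**The concern.** A power figure describes one outcome, one comparison and one test. Section 6.1 refers to the whole trial and to a single placebo arm and a single vaccine arm, so its comparison is pooled over HIV status. Section 6.3 splits the same women into two strata and tests each separately. It gives no pooled safety comparison and no comparison combined over strata, for any endpoint.

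The same section handles immunogenicity consistently. There the power is stated for 75 women per group, which matches the planned comparisons of Groups 1 v 2 and 3 v 4. Only the safety statement is out of step with its analysis.

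At stake is how a null safety result will be read. If preterm birth really rose from 10% to 22%, each stratum's test would more likely than not miss it. The non-significant result would then stand beside a stated 80% power that does not apply to it, and could be taken as reassurance.

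**Working it through.** **Inputs**
- Rates: 10% placebo, 22% vaccine (Section 6.1).
- Size: 150 v 150 pooled, 75 v 75 within a stratum (Sections 6.1 and 9.3), allocated 1:1 (Section 7).
- Level: 5% (Section 6.3). Sidedness is not stated; two-sided is assumed, and one-sided values are also shown.
- Test: Fisher's exact (Section 6.3).

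**Reproducing the protocol's figure**

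Mean rate = (0.10 + 0.22)/2 = 0.16. Variance terms: 2 × 0.16 × 0.84 = 0.2688 under the null; 0.10 × 0.90 + 0.22 × 0.78 = 0.2616 under the alternative.

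Required n per arm for 80% power:

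n = [1.96 × √0.2688 + 0.8416 × √0.2616]² / 0.12² = (1.0162 + 0.4305)² / 0.0144 ≈ 145.3, so 146 per arm or 292 in total.

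Power with n per arm = Φ{[0.12 − 1.96 × √(0.2688/n)] / √(0.2616/n)}:
- n = 150: Φ{(0.12 − 0.0830)/0.0418} = Φ(0.887) = 81.2%.
- n = 75: Φ{(0.12 − 0.1173)/0.0591} = Φ(0.045) = 51.8%.

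The stated 80% is therefore the pooled 150 v 150 figure.

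**Power at 10% v 22% by method**

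The Fisher values come from full enumeration of the two binomial distributions, counting tables with p ≤ 0.05.

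| Method | 150 v 150 | 75 v 75 |
|---|---|---|
| Normal approximation, two-sided | 81.2% | 51.8% |
| Arcsine, two-sided | 82.2% | 53.1% |
| Continuity-corrected, two-sided | 76.6% | 42.8% |
| Fisher exact, two-sided | 77.5% | **43.7%** |
| Fisher exact, one-sided | 86.1% | 56.7% |
| Normal approximation, one-sided | 88.6% | 64.2% |

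No variant reaches 80% at 75 v 75. Even pooled, the two-sided Fisher test falls slightly short of 80%.

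**What the two strata give together** (independent, same rates in each)
- Significant in both: 0.437² = 19.1%.
- Significant in at least one: 1 − (1 − 0.437)² = 68.3%.

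**Detectable rate at 75 v 75, two-sided Fisher, 10% on placebo**
- 28%: power 75.9%.
- 29%: power 80.0%.
- 30%: power 83.7%.

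**Combined analysis of the same 300 women**

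A CMH test over two strata of 75 v 75, with 10% v 22% in each, has 81.9% power and a 5.0% rejection rate under the null (200,000 simulated trials).

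**Cross-check on immunogenicity**

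With SD 2.55 log-e units and 75 per group, the standard error is 2.55 × √(2/75) = 0.416. Power for a 3.24-fold difference is Φ(ln 3.24/0.416 − 1.96) = Φ(0.863) = 80.6%. That statement agrees with its own per-group comparison.

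**The case against.** The strongest reply is that Section 6.1 contains no miscalculation. Its 80% is correct for the pooled comparison it describes, the sample size was set by feasibility, the analyses are mainly descriptive, and prematurity is offered only as an example. All of that stands. It means that the number of women need not change and that the fault is a mismatch between two sections. The protocol nevertheless states a power, a significance level and named tests, and these should describe the same analysis.

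Three further points have some force.
- Section 6.3 leaves detailed and additional exploratory analyses to the SAP, which is not available here and might add a pooled comparison. However, the protocol itself labels the within-stratum tests as the primary analyses.
- No test of prematurity alone is written, so 43.7% is the power of the specified kind of test if applied to prematurity. That is correct, and it is part of the problem: the powered outcome has no analysis of its own.
- The chance of significance in at least one stratum is 68%. For detecting harm that is a fairer figure than 19% for both, but it is still below 80% and relies on an either-stratum rule that is neither specified nor adjusted for two tests.

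The per-group exact intervals and the stopping rule on early premature labour or membrane rupture (Section 8.7) give some protection. The intervals describe each group, not the difference between groups, and the rule covers only the 14 days after vaccination. Stratum-specific reporting is reasonable given the hypothesis about HIV status, and a combined analysis need not displace it.

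**Conclusion.** The concern holds. The 80% applies to a pooled 150 v 150 comparison that this protocol does not specify. The specified two-sided Fisher test at 75 v 75 has about 44% power for 10% v 22%, and reaches 80% only at about 29% in the vaccine group.

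These figures assume a two-sided 5% level, full data on all 75 women per group, and the protocol's own rates applied equally in both HIV strata (it gives no stratum-specific rates). Loss to follow-up would lower them. A one-sided test would raise the within-stratum Fisher power to 56.7%, which does not change the conclusion. As this is the only power statement for the primary objective, it should be corrected before any results are interpreted.

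**What to change.** Preferred: in Section 6.3, add for each primary safety endpoint a GBS6 v placebo comparison stratified by HIV status, as the main comparison. Use a Mantel-Haenszel risk difference with 95% confidence interval and a CMH test; HIV status is already the randomisation stratum. Keep the within-stratum Fisher tests as supportive. Name preterm birth, as delivery before 37 0/7 weeks (the cut-off Section 8.3 already uses for prior premature delivery), as an analysed outcome within maternal primary endpoint 4. Section 6.1 can then keep its claim, restated for the CMH test at about 82% and with the assumption of equal rates in both strata made explicit.

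Alternative: if only the within-stratum tests are kept, restate Section 6.1 as about 44% power per stratum for 10% v 22%, or 80% power for 10% v 29%, by two-sided Fisher's exact test with 75 per group.

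Either way, state whether the 5% level is one- or two-sided. The cost is protocol and SAP wording plus, for the preferred route, one added analysis per endpoint. No more participants are needed, and gestation at birth is already collected (Section 9.2).
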